severity and monitor symptom changes and effect of treatment over time. It is comprised of 7 items with an unscored item which assesses patient-rated global impression their symptom related impairment. The scores range from 0-21 with cutpoints at 5, 10, and 15 for mild, moderate, and severe anxiety, respectively. A cutoff of 10 has a sensitivity for generalized anxiety disorder of 89% and specificity of 82% with test-retest reliability of ICC=0.83 [52, 55]. Patients who score ≥ 10 on the GAD-7, indicating at least moderate levels of anxiety, will be eligible for enrollment if their ED provider agrees with the high likelihood of LRCP-A. We plan to delay informed consent until after the GAD-7 determination for practical purposes as having knowledge regarding the study objective may affect the patient's responses the GAD-7. Patients will have opportunity to consent to retain the collected information as well as continue on with the study. For ineligible subjects, we will only retain counts and total scores for feasibility calculations but no identifiable information will be kept. For eligible patients, trained research personnel (investigator, research assistant, or social worker) will discuss the results of the screening tests with the patient and introduce the study and a research assistant or coordinator will obtain informed consent for assignment from interested subjects. Those who enroll will answer questionnaires assessing the domains presented and described further in table 2 below.

Outcome assessments:

1. Protocol feasibility will be assessed via patient eligibility, recruitment, and retention.
 - a. Rate of eligible patients: # of eligible patients per month based on heart score, and the % of those patients who have an eligible GAD-7 score. We believe that 30% of subjects screened will be eligible for enrollment based on prior work.
 - b. Proportion of eligible patients who enroll. Based on prior work with this population in an observational study, our target is 40%.
 - c. Proportion of enrolled patients with an intervention session or follow up visit. We aim to have 75% of those assigned to MBSR complete at least 1 session.

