4. **Treatment enactment**—Mechanisms of action specific to mindfulness as assessed with the Toronto Mindfulness Scale (TMS)[60] and the Cognitive and Affective Mindfulness Scale (CAMSR)[61] will be measured to assess intervention receipt and enactment.

6. Reporting of Adverse Events or Unanticipated Problems Involving Risk to Participants or Others

All adverse and severe adverse events will be reported in compliance with IU regulations. Some anticipated adverse events include discomfort with the subject material and psychological distress when thinking about stressful events. Participants will be able to decline to answer any questions or withdraw at their discretion, which will help to alleviate this risk. Subjects found to have severe depression at any time point as assessed by a PHQ-8 score > 19 will be referred for depression specific treatment. Subjects who disclose suicidal ideation or have active psychotic symptoms during the initial ED interview will not be eligible for continued participation and will be directed to seek appropriate care in the Emergency Department. If they disclose suicidal ideation or exhibit active psychotic symptoms at follow up the PI will be immediately contacted to evaluate for the need for intervention (referral to the ED, notification of the PCP etc.). There is also a risk for loss of confidentiality. Participants' paper and electronic records will be appropriately protected to help minimize this risk.

7. Study Withdrawal/Discontinuation

Participants will be able to withdraw themselves from the study at any point in time without issue. The PI may withdraw the patient from this study if the participant is unresponsive and/or unable to participate in a timely manner.

8. Statistical Considerations

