The goals are to collect preliminary data regarding the feasibility and effectiveness of the MBSR referral and approach compared with standard of care referral. Eligibility, recruitment, and retention information will be tabulated. Frequencies and percentages will be summarized by group for categorical variables, and continuous and count variables will be summarized by group using the mean, standard deviation, and range. The primary outcome of interest will be a comparison of the mean change in GAD-7 scores at 3 months using the t-test. Secondary analysis will look at the comparison of mean change in GAD-7 longitudinally using repeated measures ANOVA. The repeated measures ANOVA will compare scores between groups and compare scores over time within groups. Similar analyses will be used for the other efficacy outcomes. The proportion of subjects with a visit, time to first visit, and number of visits will be compared using chi-square, log-rank, and Wilcoxon rank sum tests, respectively. A 5% significance level will be used for all tests.

Because there is minimal published data to guide power calculations in this population for our outcome of interest we have chosen a sample size of 12 for each interventional arm in this pilot study on the basis of feasibility as described by Julious [62]. This sample size of 12 will be increased to 20 per arm to account for an

[name]

estimated 40% drop out rate prior to completion of the MBSR intervention. Thus, the total number of subjects we expect to enroll to the intervention is 40. All subject data will be analyzed on an intention to treat basis.

9. Privacy/Confidentiality Issues

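### Section 7 lets an investigator not blinded to arm withdraw subjects from the whole study for non-participation and does not say follow-up continues, so GAD-7 scores needed for intention to treat could be lost unequally by arm

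*Combined protocol and SAP*

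**What the plan says.** Section 7 (Study Withdrawal/Discontinuation) gives subjects the right to leave at any time and then adds: "The PI may withdraw the patient from this study if the participant is unresponsive and/or unable to participate in a timely manner". It names no arm, activity or time limit, and does not say what happens to a withdrawn subject's later follow-up.

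Section 8 (Statistical Considerations) sets the analysis: "The primary outcome of interest will be a comparison of the mean change in GAD-7 scores at 3 months using the t-test". It also states: "All subject data will be analyzed on an intention to treat basis". It does not say how a missing 3-month score enters the t-test.

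Other parts of the plan bear on the point:

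- **Assignment and blinding (Section 4).** Arm depends on the enrolment period. The only blinding described is of potential enrollees, and it ends at consent.
- **Burden (Section 5).** Both arms have evaluations at 45 days and 3, 6 and 12 months. Only Arm 2 also has eight weekly sessions of 2.5 hours and a 7-hour retreat.
- **Expected attendance (Section 5, Aim 1, items 1c and 1d).** "We aim to have 75% of those assigned to MBSR complete at least 1 session"; the target for at least six of the eight sessions is 70%.
- **Record review (Sections 5 and 10).** Two physicians review the records of every enrolled patient, and chart review or patient contact is planned at all four time points.

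**The concern.** Intention to treat needs an outcome from each assigned subject, whether or not the treatment was taken up. Section 7 allows removal on a ground that arises after assignment and reflects the subject's behaviour, at the discretion of someone who can know the arm. Because the two conditions are joined by *and/or*, inability to take part is enough by itself. A subject who answers every survey but misses classes could be withdrawn under the wording as it stands.

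GAD-7 is self-reported, so on a plain reading withdrawal from the study means no 3-month score. Arm 2 offers more occasions to fall short, and interventionists' field notes record uptake there (Section 5, Fidelity Monitoring). If those removed have a different prognosis from those kept, and removals are unequal between arms, the 3-month comparison is biased. With 20 subjects per arm, a handful of removals matters.

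**Working it through.** **1. The plan's own figures.** Section 8 starts from 12 per arm and allows for 40% dropout: 12 / (1 − 0.40) = 20 per arm, 40 in total, as stated. Section 5 assumes 10% loss at each of four time points: 0.9⁴ = 0.656, which agrees with the stated 65%. The base of 12 is a rule of thumb, so there is no power figure to reproduce.

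**2. How many Arm 2 subjects could the clause reach?** The documents give no PI-withdrawal rate. As stand-ins I use the complements of the two attendance targets and the dropout allowance:

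| Stand-in for share removed, *f* | Removed of 20 | Left |
|---|---|---|
| No session attended, 25% | 5 | 15 |
| Fewer than six sessions, 30% | 6 | 14 |
| Dropout allowance, 40% | 8 | 12 |

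**3. Worst-case bias.** Assume no true effect, the same share *f* of poorer-prognosis subjects in both arms, all of them removed from Arm 2 and none from Arm 1, and all able to answer had they been kept. If they improve *d* points less, the mean improvement of those kept exceeds that of the full arm by *f* × *d*. The documents do not give *d*; I assume 2 to 4 points. The standard error uses an assumed SD of change of 5: 5 × √(1/20 + 1/n), with n the number left in Arm 2.

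| *f* | *d* | Bias *f* × *d* | Standard error | Bias / SE |
|---|---|---|---|---|
| 0.25 | 2 | 0.5 | 1.71 | 0.29 |
| 0.30 | 3 | 0.9 | 1.74 | 0.52 |
| 0.40 | 4 | 1.6 | 1.83 | 0.87 |

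The bias favours MBSR only because *d* is assumed positive. If those removed improved as much as the others it is zero; if they improved more it reverses.

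**4. What happens when Arm 1 also loses subjects.** If Arm 1 loses a share *q* of its subjects, all of poorer prognosis, the bias is *d* × (*f* − *q*) / (1 − *q*).

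| *f*, *d* | *q* = 0 | *q* = 0.10 | *q* = 0.20 | *q* = *f* |
|---|---|---|---|---|
| 0.25, 2 | 0.5 | 0.33 | 0.13 | 0 |
| 0.30, 3 | 0.9 | 0.67 | 0.38 | 0 |
| 0.40, 4 | 1.6 | 1.33 | 1.00 | 0 |

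A *q* of 0.20 is close to two time points at the plan's 10% loss: 1 − 0.9² = 0.19.

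**5. Would withdrawals fall mainly on Arm 2?** The Arm 2 share of withdrawals is *f* / (*f* + *q*). For *f* from 0.25 to 0.40 it is 100% if *q* = 0, 57% to 68% if *q* = 0.19, and 38% to 50% if *q* = 0.40. The documents do not settle which applies.

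**The case against.** The strongest reply is that the clause is neutral between arms and opens with unresponsiveness, which most naturally means failing to answer follow-up contacts, and these are the same in both arms. Elsewhere the plan does not treat missed sessions as leaving the study: MBSR is offered as a referral, surveys are paid for whether or not classes are attended, and attendance is reported over everyone assigned to MBSR. All of that stands, and it rules out several stronger readings that a reader might infer:

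- *The clause mainly removes MBSR non-attenders, so the comparison becomes attenders against all controls.* This would need every Arm 2 non-attender and no Arm 1 subject to be withdrawn. No text says so.
- *Record-based outcomes are lost.* Sections 5 and 10 plan record review for enrolled patients and do not say that it stops at withdrawal. Its continuation is unstated, which is less than a loss.
- *The plan itself expects 25% to 40% to be withdrawn.* Those figures are complements of attendance targets and a dropout allowance that Section 8 applies to both arms.
- *Section 7 contradicts intention to treat.* Section 8 covers all subject data, and nothing says that withdrawn subjects' data are discarded.

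A subject who truly cannot be reached also gives no score with or without formal withdrawal. Only those who would have answered are lost because of the clause, and their number is unknown. If there are none, the bias due to the clause is zero.

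The reply does not remove the point that the wording permits removal of a subject who is still answering, and that no text keeps such a subject in follow-up.

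**Conclusion.** The concern holds as a defect in a stated rule. Section 7 permits discretionary removal from the whole study on undefined grounds after assignment, and nothing secures the GAD-7 scores that Section 8 needs. Unequal removal by arm is plausible because only Arm 2 has sessions and a retreat to miss, but it is an inference.

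The size and direction of any bias cannot be determined from the documents. The range of 0.5 to 1.6 GAD-7 points in favour of MBSR is a worst-case illustration. It rests on the assumed prognosis gap of 2 to 4 points, removals of 25% to 40% confined to Arm 2, and every removed subject otherwise answering. The assumed SD of 5 affects only the standard errors. The bias falls towards zero as Arm 1 loses similar subjects.

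This is a 40-subject pilot meant to give preliminary data, so the defect does not invalidate the design. It should still be corrected, because the correction is cheap and the lost scores cannot be recovered later.

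**What to change.** Amend Section 7 to separate stopping the course from leaving the study:

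- Limit PI withdrawal for non-participation to ending MBSR sessions.
- State that missed sessions or missed contacts do not end follow-up.
- State that survey attempts at each time point and record review to 12 months continue in both arms unless the subject withdraws consent.

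In Section 8, state that all assigned subjects are analysed in their assigned arm, and say how a missing 3-month GAD-7 score is handled.

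The cost is a few sentences and some extra contact attempts. Telephone, mail and online surveys and chart review are already in the plan, so no new procedure is needed.

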Specific Aim 1: To determine the feasibility of employing rapid cardiac risk stratification and psychological screening to identify patients with LRCP-A in the ED for subsequent referral to MBSR. Currently there are no tools regularly used in the ED to screen for LRCP-A, however, our *working hypothesis* is that evidence-based tools can be used to identify patients at risk for LRCP-A. To accomplish this, we will execute

[name]

a two-step prospective screening approach: 1. Determine score on the validated and widely used HEART scale [50, 51]. 2. Those with a HEART score <4 will complete the General Anxiety Disorder 7-item (GAD-7) questionnaire. Scores ≥ 10 are indicative of the criterion standard for moderate to severe symptoms of anxiety [52]. In this pilot study, feasibility will be assessed in a number of ways including the determination of the rate of eligible subjects per month, proportion of eligible subject who enroll, and proportion who complete the MBSR intervention. *Expected outcome:* This aim is designed to provide data regarding the feasibility of the risk stratification, psychological screening, and MBSR referral approach.

Specific Aim 2: To determine the effect of an MBSR training program for patients with LRCP-A on mental health (longitudinal GAD-7 scores, quality of life (PROMIS Global Short Form), and ED resource utilization (return ED visits). *Our working hypothesis* is that early referral to MBSR will help patients better regulate their thoughts, feelings, and bodily sensations related to their anxiety symptoms and have a significant positive effect on patient-centered outcomes such as mental health, quality of life as well as decreased ED resource utilization. To this end we will assign LRCP-A patients identified in SA1 to usual care referrals versus MBSR. We will then follow these patients for outcomes including change in GAD-7 scores, PROMIS Global Short Form, ED utilization among other outcomes at 6 weeks, 3 months, 6 months, and 1 year. *Impact:* This aim will establish a viable and novel treatment pathway for ED patients identified to be at risk for LRCP-A to ensure the possibility of early directed intervention.

3. Inclusion/Exclusion Criteria

Inclusion:

- Age: 18 through 70
- Chief complaint of chest pain
- HEART Score of 0-3 indicating Major Adverse Cardiac Events (MACE) risk equivalent to $\leq 2\%$
- GAD-7 score ≥ 10

Exclusion:

- Age <18 or ≥ 71
- Chief complaint of anxiety, panic, or similar

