- Prior personal ACS history (known at time of provider interview)
- Previous enrollment in the study
- Traumatic injury to the chest
- Suicidal ideation or active psychosis or behavioral issues requiring psychiatric monitoring
- Hemodynamic instability
- Non-English speaking
- Potential issues affecting follow up
 - Prisoners, homeless patients, out-of-town residences

4. Enrollment/Group Assignment

We will screen patients presenting to the Methodist ED with the chief complaint of chest pain. Sources for this information include the ED tracking systems and electronic medical records systems. Patients will be evaluated with the HEART score by their treating physician to determine if the patient initially qualifies to participate in the study. The treating physician will provide the information necessary to calculate the HEART score. Qualifying subjects will then be approached for final eligibility assessment using the GAD-7 and consented if interested and eligible.

Enrolled subjects will be assigned to either arm depending upon enrollment period. In the 8 weeks prior to the MBSR course commencement all subjects enrolled will be assigned to Arm 2: MBSR. This period will be immediately followed by 8 weeks of enrollment in Arm 1: Standard Referral. To decrease subject bias with regard to the interventional arm, potential enrollees will remain blinded to the enrollment period until informed consent is complete. This method of assignment has been chosen to help maximize intervention enrollment given the limited recruitment period.

5. Study Procedures (see figure 1 for an overview of protocol)

[figure not shown]
Figure 1 illustrates an overview of the flow of screening and enrollment for both specific aims. The patients who screen eligible in Aim 1 are the population of interest for assignment in Aim 2. The goal is to assign 40 subjects for the intervention arms. Each enrolled subject will have follow up evaluations at 45 days, 3 months, 6 months, and 1 year. Two ED physicians will independently review medical records of each enrolled patient for the described outcome variables and adjudicate any discordances by consensus.

Specific Aim 1: To determine the feasibility of employing rapid cardiac risk stratification and psychological screening to identify patients with LRCP-A in the ED for subsequent referral to MBSR.

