8	The rest of your life: Making the practice your own	
 ▪ Body scan ▪ MM ▪ Sitting meditation 	
 ▪ Review of the course with an emphasis on daily strategies for maintaining and deepening mindfulness skills ▪ Sharing of participant perspectives on the program; welcoming all comments 	
 ▪ Mindfulness resources handout ▪ Continuing the practice & making it your own ▪ Bringing seamless attention to life

Outcome assessments: The schedule of assessments is shown in Table 2. These assessments will take place in the method most convenient for the patient (telephone, mail, or online REDCap survey completion). These are all methods the PI and his research team are currently using. **The primary outcome of interest will be the mean longitudinal change in GAD-7 scores between intervention groups at each time point.**

Domain	Measure	# of Items	Time Period Investigated				
			ED	45 day	3 mo	6mo	12mo
MACE [†] Risk	HEART Score	5	x				
ACS Risk	PreTest Consult ACS	8	x				
Demographics	Age, Race, Gender, Education etc.	10	x				
Medication Use	Standard Items	2	x	x	x	x	x
Medical Comorbidity	9-Condition Checklist	9	x				
Chest Pain Symptoms	Custom Items and Numeric Rating Scale	5	x				
Somatization	Patient Health Questionnaire (PHQ-15)	15	x	x	x	x	x
Anxiety Severity	Generalized Anxiety Disorder Scale (GAD-7)	7	x	x	x	x	x
Panic	PHQ Panic Scale	5	x	x	x	x	x
Social Anxiety	Mini-SPIN	3	x	x	x	x	x
PTSD	4-Item screen	4	x	x	x	x	x
Depression	Patient Health Questionnaire (PHQ-8)	8	x	x	x	x	x
Cardiac Anxiety	Cardiac Anxiety Questionnaire	18	x	x	x	x	x
Resilience	Brief Resilience Scale	6	x				
Pain Catastrophizing	Pain Catastrophizing Scale	13	x				
Healthcare Utilization (12 mo Pre-ED)	Custom Items	6	x				
Healthcare Utilization (Post-ED assessment)	Custom Items	6		x	x	x	x
Healthcare Related Quality of Life	PROMIS Global Short Form	10	x	x	x	x	x
Life Trauma	Traumatic Life Events Questionnaire	18	x				
MBSR Mechanism of Action	Cognitive and Affective Mindfulness Scale-Revised (CAMS-R)	10	x	x	x	x	x
MBSR Evaluation	Toronto Mindfulness Scale (TMS)	13	x	x	x	x	x

[†]Major Adverse Cardiac Event

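### The primary t-test on GAD-7 change does not adjust for baseline GAD-7, so a baseline gap between the two enrolment-period arms passes in part into the arm difference

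*Combined protocol and SAP*

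**What the plan says.** Section 8 (Statistical Considerations) names the primary analysis: "The primary outcome of interest will be a comparison of the mean change in GAD-7 scores at 3 months using the t-test". The secondary analysis is also unadjusted: "The repeated measures ANOVA will compare scores between groups and compare scores over time within groups". The same approach extends to the other scales: "Similar analyses will be used for the other efficacy outcomes". Section 5 (Specific Aim 2, outcome assessments) words the primary outcome differently: "The primary outcome of interest will be the mean longitudinal change in GAD-7 scores between intervention groups at each time point". That wording names no baseline covariate either, so the point holds under both.

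Three design features bear on this:

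- **Allocation is by calendar period.** Section 4: "Enrolled subjects will be assigned to either arm depending upon enrollment period". The MBSR period comes first, and "This period will be immediately followed by 8 weeks of enrollment in Arm 1: Standard Referral".
- **Entry is selected on the outcome scale.** Section 3 lists "GAD-7 score ≥ 10" as an inclusion criterion, and Section 5 repeats it: "Patients who score ≥ 10 on the GAD-7, indicating at least moderate levels of anxiety, will be eligible for enrollment".
- **Baseline is available for everyone.** The GAD-7 is self-reported, taken in the ED before consent and needed for eligibility. Potential enrollees do not know the period until consent is complete.

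**The concern.** A t-test on change fixes the slope of follow-up on baseline at 1. Patients enter because one ED measurement was high, on a scale whose test-retest ICC the protocol gives as 0.83, so a slope below 1 is to be expected. Higher scorers at entry will then tend to fall further without any treatment effect.

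Regression to the mean that is common to both arms cancels in the comparison. The part tied to a difference in baseline means does not. Here nothing balances those means even in expectation, and the arms are small. At stake is the headline estimate of a pilot whose Section 8 goals include preliminary effectiveness data and which tests at 5%. Part of that estimate could reflect who happened to score higher at entry, and the plan has no prespecified way to take that part out.

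**Working it through.** **The plan's own figures.** Enrolment: 12 / (1 - 0.40) = 20 per arm, 40 in total, which reproduces Section 8. There is no power, effect size or SD to reproduce. Section 5 assumes 10% loss at each follow-up. Month 3 is the second, so 20 x 0.9 x 0.9 = 16.2, or about 16 per arm with a 3-month score.

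**Assumptions, because the documents give no SD or 3-month correlation.** GAD-7 among those screened is taken as normal with mean 6.6 and SD 5.5, rounded and clipped to 0-21. About 30% then score 10 or more. Section 5 expects 30% of those screened to be eligible; reading that as the GAD-7 pass rate is itself an assumption. The correlation r between baseline and 3 months, before selection, is set at 0.3, 0.5 and 0.7, with 0.83 (the documented reliability) as an upper end. Selection at 10 or more leaves a baseline SD of 2.73.

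**Shift from a baseline gap.** Shift = (1 - slope) x g.

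**Chance range of the gap at 20 per arm.** 1.96 x 2.73 x sqrt(2/20) = 1.69 points.

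| r | slope among entrants | shift, 2-point gap | shift, 1.69-point gap | SE of change difference, 16 per arm | shift / SE |
|---|---|---|---|---|---|
| 0.3 | 0.29 | 1.4 | 1.2 | 1.88 | 0.64 |
| 0.5 | 0.49 | 1.0 | 0.86 | 1.71 | 0.50 |
| 0.7 | 0.70 | 0.6 | 0.51 | 1.40 | 0.37 |
| 0.83 | 0.83 | 0.34 | 0.29 | 1.09 | 0.27 |

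Ratios use unrounded slopes. At a one-SD gap (0.86 points) they are about half as large: 0.32, 0.25 and 0.19 for the first three rows. If the chance range is also taken at 16 per arm (1.96 x 2.73 x sqrt(2/16) = 1.89 points), they become about 0.7, 0.6 and 0.4.

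**Type I error.** With both arms drawn from the same population and no effect, the t-test rejected in 4.5-5.6% of simulated trials. A separate simulation held the observed gap fixed (12 per arm, normal scores, SD 3 at both times, no effect):

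| r | t-test, gap 0 | t-test, gap 2 | ANCOVA, gap 2 |
|---|---|---|---|
| 0.3 | 1.7% | 10.7% | 5.5% |
| 0.5 | 2.2% | 9.7% | 5.5% |
| 0.7 | 3.5% | 7.6% | 4.8% |

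The t-test is therefore right on average over chance gaps, but not for a given gap. A gap that the periods produce systematically does not average out.

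**Net precision.** Simulated 95% CI half-widths under the selected-entry model, including the cost of estimating the slope:

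| r | 16 per arm: t-test / ANCOVA | 12 per arm: t-test / ANCOVA |
|---|---|---|
| 0.3 | 3.83 / 3.62 | 4.49 / 4.28 |
| 0.5 | 3.47 / 3.38 | 4.04 / 3.97 |
| 0.7 | 2.84 / 2.83 | 3.33 / 3.35 |

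That is about 5% narrower at 0.3, about 2% at 0.5 and no gain at 0.7. At 0.83 the ANCOVA interval is 1-2% wider.

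**The case against.** The strongest reply is that this is a feasibility pilot with no power claim, that a t-test on change is valid when imbalance is due to chance, and that its standard error already contains that chance variation. All of this stands. A chance gap should not be charged once as bias and again as a wider interval. The group summaries (mean, SD, range) would also let a reader see a baseline gap if they are reported for baseline GAD-7.

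It is also true that ANCOVA does not rescue a non-randomised comparison. Entry depends on the ED provider's agreement that anxiety-related chest pain is likely, as well as on GAD-7. Section 4 blinds potential enrollees to the period but does not mention staff. Selection could differ between periods on factors that no baseline score captures. In that case change scores and ANCOVA each rest on assumptions that the data cannot test.

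None of this favours leaving the slope fixed at 1. Seeing a gap in a table does not correct the estimate, and an adjustment added after the gap is seen would look data-driven.

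A reader might infer a large precision gain from the textbook variance ratio (1 + r)/2, which gives 0.65 at r = 0.3. That ratio assumes equal SDs at baseline and follow-up, and the entry cut-off narrows the baseline. With SDs of 3 and 5 the ratio is 0.91 at r = 0.3 and about 0.98-0.99 at 0.5 to 0.7, before the cost of estimating the slope.

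**Conclusion.** The concern holds as a worthwhile improvement of modest size. The unadjusted change-score comparison lets a realised or systematic baseline GAD-7 gap between the periods into the primary estimate. The shift is about 0.6 to 1.4 points for a 2-point gap at r = 0.7 to 0.3. At the edge of the chance range for 20 per arm it is about 0.4 to 0.6 SE, or about 0.3 SE if r is as high as 0.83. These sizes rest on the assumed distribution and correlations. The 2-point gap is also an assumption, because the documents give no figure for a period difference.

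A reader might infer that an ordinary gap moves the result by nearly a full standard error. When shift and SE are taken at the same correlation, no scenario reaches that, and the 1.7-point gap is the 95% edge rather than a typical value. A reader might also infer that the planned test has an inflated error rate as it stands. That would need a systematic period difference, which the documents neither state nor rule out. The sample size of 20 per arm is unaffected. The case for adjustment rests on the gap, not on precision.

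**What to change.** In Section 8, replace the primary t-test with wording such as: *The 3-month GAD-7 score will be compared between arms by linear regression on arm and ED baseline GAD-7, reported as the adjusted mean difference with 95% CI. The unadjusted t-test of change will be supportive.* Use the same form for the other scales that have an ED baseline in the Section 5 schedule of assessments.

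Add one limiting sentence: *This adjusts for measured baseline GAD-7 only and does not remove calendar-period or other unmeasured differences between the arms.*

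The cost is this wording and one degree of freedom, with an interval that may be very slightly wider if the correlation is 0.7 or above. No new data or patients are needed.
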